2.2.3 Secondary efficacy variables

2.2.3.1 Derivation of secondary [REDACTED] variables

Rate of glycemic control over time

[figure not shown]
The rate of loss of glycemic control over time will be estimated by an annualized slope of HbA1c over time from Visit 5 (Week 26) to the end of Period 1. A mixed effect model

including a random coefficient will be used for analysis. The rationale of choosing Visit 5 as starting point for estimating the rate (slope) of loss of glycemetic control over time is based on data from study CLAF237A2307 (Scherbaum W et al, 2008) where the maximal reduction in mean HbA1c from baseline was between 24 and 32 weeks, therefore a trend for loss in glycemetic control is sensible to be estimated from a similar time point.

In the analysis of the rate of loss in glycemetic control over time, data used in analysis will be censored at the start of Period 2, i.e. the only data included in the model will be from Visit 5 (Week 26) to the end of Period 1.

FPG

If the FPG value (standard non meal-test parameter) is missing, the -20 min meal-test value (obtained on the same day) can be used to impute. If the -20 min value is also missing, the 0 min value will be used.

Calculation of OGIS

OGIS will be calculated as a function of glucose and insulin (meal-test laboratory parameters):

$$\text{OGIS} = 0.5 * \{ \\ \quad [(P_5 * (G(90) - G_c)) + 1] * CI_OGTT] \\ \quad + \text{sqrt} \{ \\ \quad \quad [(P_5 * (G(90) - G_c)) + 1] * CI_OGTT] ^2 \\ \quad \quad + [4 * P_5 * P_6 * (G(90) - G_c) * CI_OGTT] \\ \quad \quad \} \\ \quad \}$$

where,

- $CI_OGTT = \{ P_4 * \{ (P_1 * D_0) - [V * (G(120) - G(90))] / 30 \} / G(90) + (P_3 / G(0)) \}$
 $/ \{ I(90) - I(0) + P_2 \}$
- D_0 (g/m²) is the glucose dose included in the standard meal administered to patients who participate in the standard meal-test ($D_0 = (73.2 * 5.551) / BSA$ for the standard meal as planned in [Protocol Section 6.4.3](#). It will be assumed all patients receive a standard meal),
- $BSA = 0.164 * (\text{Weight in kg} ** 0.515) * ((0.01 * \text{Height in cm}) ** 0.422)$,
- $V = 10000$ (ml/m²) is the assumed glucose distribution volume,
- $G(0)$, $G(90)$ and $G(120)$ are glucose concentration values (taken from meal-test laboratory data) at timepoints 0, 90 and 120 min,
- $I(0)$ and $I(90)$ are insulin concentration values (taken from meal-test laboratory data) at timepoints 0 and 90 min,
- $P_1=6.5$, $P_2=1951$, $P_3=4514$, $P_4=792$, $P_5=0.0118$, $P_6=173$, $G_c=5$ are constants ([Mari, et al 2001](#)).

If the value of glucose or insulin values at 0 minutes are missing, then the -20 min meal-test value (obtained on the same day) can be used to impute. If the -20 min value is also missing, the fasting parameter result (i.e. standard non meal-test parameter) will be used. Both glucose and insulin should be imputed using the same timepoint (regardless if one has value available).

No imputation will be used for missing 90 or 120 minute values.

Calculation of ISR

Separately for each patient and each meal-test, deconvolution is applied to estimating insulin secretion to assess β -cell function. C-peptide, which is co-secreted with insulin in an equimolar ratio, is preferred to insulin as a basis for estimating insulin secretion.

Mathematically, we need to solve for the insulin secretion rate r given the impulse response h , and plasma C-peptide c , where

$$c(t) = \int_{-\infty}^t h(t-s)r(s)ds.$$

The impulse response is the PK model for an intravenously administered unit bolus dose of C-peptide when the endogenous C-peptide production has been suppressed, i.e.

$$h(t-s) = (1/V)[f e^{-\alpha(t-s)} + (1-f)e^{-\beta(t-s)}],$$

where V , f , α , and β are a subject's parameters, which are generally unknown. However, from clinical studies these parameters have been estimated, and are related to a subject's disease status, body surface area, age, and gender. Thus, h becomes known.

Insulin secretion rates are modeled by a piecewise continuous linear function with knots at the actual sampling time. Changes in slopes are penalized through a single regularization parameter that is determined by a root finding method to produce similar residual standard deviation for fitted C-peptide concentrations as would be expected from assay error standard deviations given in the kit instructions.

The IMMULITE 2000 C-peptide kit instructions were used to model intra-assay SD as a function of the true C-peptide concentration $C1$ expressed in conventional units of ng/mL by simple linear regression as:

$$SD = 0.04056C1 + 0.06311\text{ng/mL.}$$

With concentration of C-peptide expressed alternatively in SI units, i.e., $C2$ expressed in nM (1ng/mL C-peptide = 0.331nM C-peptide) the equations for SD becomes:

$$SD = 0.04056 C2 + 0.331 \times 0.06311\text{nM.}$$

The following ln-transformation with a shift parameter of observed and fitted C-peptide values is used to stabilize the variance in performing the deconvolution:

$$\ln(C1 + 0.06311/0.04056) \text{ or } \ln(C2 + 0.331 \times 0.06311/0.04056).$$

Nonlinear least squares with ISR constrained non-negative using PROC IML function NLPLM in SAS® is used to solve for ISR at the sampling time points using actual sampling times. The bisection method is used to iteratively determine the regularization parameter such that the sum of squares of the observed C-peptide minus the fitted C-peptide expressed in either units equals $0.040562n$ where n is the number of non-missing C-peptide concentrations in the meal-test.

Validated macros (ISR and ISR_IML2) have been provided by Novartis and will be used to derive the ISR in █████ production and validation programs.

Calculation of AUC

AUC of ISR/G is defined as $\text{ISR relative to glucose 0-2h (pmol/min/m}^2\text{/mM)} = \text{AUC}_{0-2\text{hr}}$ of $\text{ISR/AUC}_{0-2\text{hr}}$ of glucose. (Glucose is taken from the meal-test laboratory data).

For the patients participating in the meal-test, the laboratory parameters glucose, insulin and C-peptide are also to be measured at the following 7 time-points (minutes in relation to the meal time): -20min, 0min (immediately prior to meal ingestion), 15min, 30min, 60min, 90min, 120min. Let L_1, L_2, \dots, L_7 denote the lab measurements at these 7 time-points (i.e., L_1 is the value measured at 20min pre-meal, L_2 is the value measured at 0min pre-meal, ..., L_7 is the value measured at 2h after the meal) and T_1, T_2, \dots, T_7 be the corresponding times (actual times in units of h), the $\text{AUC}_{0-2\text{hr}}$ is calculated (using the trapezoidal rule) as:

$$\text{AUC}_{0-2\text{h}} =$$

$$[(L_2 + L_3) \times (T_3 - T_2) + (L_3 + L_4) \times (T_4 - T_3) + (L_4 + L_5) \times (T_5 - T_4) + (L_5 + L_6) \times (T_6 - T_5) + (L_6 + L_7) \times (T_7 - T_6)] / 2.$$

Note for above calculation:

- 1) L_1 and T_1 are not used in the calculation. However, if L_2 (the value at 0 min) is missing, the L_1 (the value at -20 min) will be used in its place, but T_2 should still be used in the calculation (i.e., no substitution of T_2 with T_1 is allowed). If the -20 min AND 0 min values are missing, the fasting value (i.e. the standard non meal-test value) will be used to impute the 0 min value. If the 0 minute ISR is missing due to missing 0 minute c-peptide, then the missing c-peptide value should be imputed using this approach, in order to obtain a non-missing 0 minute ISR value.
- 2) If L_i (a lab value) is not missing, but the corresponding time T_i is missing, T_i will be imputed by the planned time (or scheduled time).
- 3) If L_i is missing at a timepoint T_i , the next available value L_{i+1} and timepoint T_{i+1} will be used for calculating AUC.
- 4) AUC_{0-2h} will only be calculated for patients for whom there are at least 3 timepoints (including one of the first two timepoints (i.e., 0 or -20 min pre-meal), the last timepoint (i.e., 2 hours post-meal), and a timepoint in between) where the actual laboratory values are known.

2.2.3.2 Variable definition

The following secondary [REDACTED] efficacy variables will be analyzed. They are grouped by type of analyses for the convenience of describing the related analysis methods.

Variables related to time to event method

- Time to insulin initiation.

Variables related to the rate of change of β -cell function and insulin sensitivity

- Rate of loss of β -cell function (assessed using the AUC of ISR/G) from Visit 4 (week 13) to:
i) end of Period 1; ii) end of Period 2; iii) EOS.
- Rate of change in insulin sensitivity (assessed using the OGIS) from Visit 4 (week 13) to: i) end of Period 1; ii) end of Period 2; iii) EOS.

Variables related to the rate of loss in glycemic control over time

- Rate of loss in glycemic control in HbA1c from 26 weeks after the start of Period 2 to end of Period 2.
- Rate of loss in glycemic control in FPG, i) from Visit 5 (week 26) to: i) end of Period 1; ii) from 26 weeks after start of Period 2 to end of Period 2.

Variables related to change from baseline to endpoint

- Change in AUC of ISR/G (as an assessment of β -cell function) from baseline to: i) end of Period 1; ii) end of Period 2; iii) EOS.
- Change in OGIS (as an assessment of insulin sensitivity) from baseline to: i) end of Period 1; ii) end of Period 2; iii) EOS.

[REDACTED]

2.2.3.3 Statistical analysis methods

[figure not shown]
Rate of loss in glycemc control over time

The rate of loss in glycemc control over time will be estimated by the slope of HbA1c over time (in years) as a random coefficient in a linear mixed effect model: the model will be fitted to HbA1c data collected from Week 26 and onwards, up to and including the end of the Period 1 visit, i.e. up to and including the initial treatment failure date. It includes treatment approach, geographic region, baseline HbA1c, time (of HbA1c measurements, in years) and the interaction of treatment approach by time as the fixed effects, and time and intercept as a random effects. Treatment approach and geographic region will be considered as classification variables while baseline HbA1c and time are the covariates. The unstructured covariance will be used as the covariance structure within patients. The actual hypothesis will be tested using the treatment approach by time interaction term. Note that it is not an issue that patients who ‘fail’ at Week 26 will only contribute one data point to the analysis, as this is expected in only a few patients.

The mean slopes within each treatment approach and the difference in mean slopes between two treatment approaches as well as the p-value obtained from the test using the above model will be presented. Graphical representation will also be produced as required.

The analysis will be performed using the FAS. It will be performed in the PPS as supportive analysis as well.

The assumptions for inference using the model as described above (i.e., errors are independently normally distributed with constant variance) will be checked using CSR Section 16 table(s) by subjective examination of the presented residual plots: normal probability plot and residuals versus fitted values plots.

Variables related to the rate of change of β -cell function and insulin sensitivity over time

The rate of change of β -cell function and insulin sensitivity (assessed using the AUC of ISR/G and OGIS respectively) from Visit 4 (week 13) to the end of Period 1, or from Visit 4 (week 13) to the end of Period 2, or from Visit 4 (week 13) to the end of study will be assessed using a similar random coefficient linear mixed effect model used in the primary efficacy endpoint 'rate of loss in glyceic control in HbA1c from Visit 5 (Week 26) to the end of Period 1'.

This analysis is performed in the FAS only. Data collected up to the end of Period 1, or the end of Period 2, or to the end of the study will be used in the analysis for assessing the rate of change from Visit 4 to end of Period 1, or from Visit 4 to end of Period 2, or from Visit 4 to the end of the study respectively.

A general downward trend from Visit 4 to the end of study can be assumed for these parameters.

[figure not shown]
Variables related to the rate of loss in glyceic control over time

The rate of loss in glyceic control in HbA1c or FPG from 26 weeks after the start of Period 2 to the end of Period 2 will be assessed for patients who start insulin therapy in Period 3 (i.e. for treatment intensification) or discontinue the study during Period 2 due to not being able or unwilling to initiate insulin therapy in Period 3. The random coefficient linear mixed effect model used in the primary efficacy endpoint 'rate of loss in glyceic control in HbA1c from Visit 5 (Week 26) to the end of Period 1' will be used in this secondary variable. Only data collected between initiation of Period 2 to insulin initiation on patients who take insulin therapy in Period 3 (i.e. for treatment intensification) or who discontinued the study in Period 2 due to not being able or unwilling to initiate insulin therapy in Period 3 will be included in this model. Patients who complete the study in Period 1 or Period 2 will not be included in the analysis. The analysis will be performed in the FAS only. Note that it is not known how many patients will proceed into Period 3, so may need to later review whether the planned analysis for the subgroup of patients entering Period 3 (or being unable/unwilling to) is sensible.

The rate of loss in glyceic control in FPG from 26 weeks to the end of Period 1 will be assessed using the same random coefficient linear mixed effect model used in the primary efficacy endpoint 'rate of loss in glyceic control in HbA1c from Visit 5 (Week 26) to the end of Period 1'. This analysis is performed in the FAS only.

[figure not shown]
Variables related to change from baseline to endpoint

An analysis of covariance (ANCOVA) model with treatment approach, geographic region as classification variables and baseline value as a covariate will be used to assess all secondary efficacy variables related to change from baseline to endpoint. The least squares mean (“adjusted mean”) change from baseline for each treatment approach, the difference in the least squares mean changes between the two treatment approaches, and the two-sided adjusted 95% confidence interval along with the p-value for the difference will be obtained from this analysis model and presented.

Supportive descriptive analysis for secondary [REDACTED] variables over time

Summaries of absolute values and change from baseline to: i) end of Period 1; ii) end of Period 2; iii) EOS; in secondary [REDACTED] (including FPG, [REDACTED], AUC of ISR/G, OGIS, [REDACTED]) by treatment approach and visit will be presented in the FAS.

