3.1.3 Period 2: vildagliptin/metformin combination versus vildagliptin add-on to metformin

In the case of two consecutive HbA1c measurements $\geq 7.0\%$ from two consecutive study visits during Period 1, scheduled according to [Table 6-1](#) & [Table 6-2](#), patients in both arms will receive new vildagliptin study medication packs. The investigator will contact the IRT system within 2 weeks after the receipt of the second of the two elevated HbA1c measurements. The IRT system will assign the new vildagliptin study medication packs. Patients who were randomised to the placebo arm in Period 1 will now receive vildagliptin 50mg bid. Patients who were randomised to the active vildagliptin 50mg bid arm in Period 1 will continue to receive vildagliptin 50mg bid. All patients will continue to take their metformin dose unchanged. Period 2 will remain masked to the patient and both patients and investigators will remain masked to the treatment allocation in Period 1.

Any anti-diabetic medication other than the study regimen is not allowed during Period 2, except if the patient had temporarily reduced/interrupted the treatment regimen due to AEs or untoward events that require temporary dose adjustment/interruption (see [Section 5.5.5](#)).

If, during Period 2, therapy intensification is required in accordance with the local guidelines, the patient will enter Period 3.

The duration of Period 2 may differ between patients. End of Period 2 is considered when insulin treatment is initiated, or alternatively when the patient is discontinued because insulin treatment is not initiated in Period 3 (see [Section 3.1.4](#)).

[figure not shown]

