2.1.6 Study medication

The study consists of three treatment periods.

In Period 1 patients will be randomized to metformin + vildagliptin 50mg bid, or metformin + placebo. If initial treatment fails to maintain HbA1c < 7.0%, confirmed at two consecutive scheduled study visits (after remapping in [section 1.3.3](#) has been applied), starting from Visit 4 (Week 13), then vildagliptin will be added to metformin in the metformin-only arm in Period 2. The Period 1 end date is defined as the date of the second of the two consecutive scheduled study visits, i.e. the initial treatment failure date. The Period 2 start date is defined as the next day.

In Period 3, insulin is considered based on local guidelines. Both patients and investigators will remain masked to the treatment allocation in Period 1, and the study will compare the two different treatment approaches. The Period 3 start date is defined as the date of insulin initiation. The Period 2 end date is defined as the previous day.

Treatments are referred to as ‘Treatment approach’ throughout this analysis plan to acknowledge that patients are not on the same treatment for the duration of the study. When summaries are detailed for the ‘Treatment Period’, they will include data from Periods 1, 2 and 3, unless specified otherwise.

The duration of exposure to study medication (in months) during the treatment period will be computed for all patients using the algorithm outlined in [Section 1.4](#) and summarized by treatment approach for the RAN both descriptively (i.e., mean, standard deviation, median, minimum and maximum) and by 3 - monthly intervals (0 - < 3 months, 3 - < 6 months, ..., ≥ 60 months).

The study Period 1 duration (in months) will be also similarly summarized for the RAN. The study Period 1 duration is defined as (initial treatment failure date – treatment start date + 1)/30.4375 for patients who entered study Period 2. The study Period 1 duration is the same as overall study duration for patients who did not enter into Period 2.

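### The Period 2 HbA1c and FPG slope comparison is not a randomised comparison, yet it carries a p-value with no descriptive label, and its paragraph gives two data windows

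*SAP*

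**What the plan says.** The analysis is in SAP 2.2.3.3 (Addendum 1, with the same patients and windows in V3.0) and in protocol 9.5.2.2.

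- **Patients.** The slope "from 26 weeks after the start of Period 2 to the end of Period 2 will be assessed for patients who start insulin therapy", or who leave during Period 2 because they cannot or will not start it. The SAP adds that patients who finish the study in Period 1 or Period 2 are left out.
- **Model.** Addendum 1 reuses "The random coefficient linear mixed effect model used in the primary efficacy endpoint", meaning the Period 1 HbA1c slope. Section 2.8 of the same document had already made that slope secondary, and V3.0 describes the reuse neutrally.
- **Test.** In that model, "The actual hypothesis will be tested using the treatment approach by time interaction term". Mean slopes and their difference are reported, "as well as the p-value obtained from the test using the above model will be presented".
- **Data.** A later sentence admits "Only data collected between initiation of Period 2 to insulin initiation on patients who take insulin therapy in Period 3", plus the patients who left without insulin.
- **Design.** Under protocol 3.1.3, "Patients who were randomised to the placebo arm in Period 1 will now receive vildagliptin 50mg bid", while the combination arm continues unchanged. The same section fixes when the period closes: "End of Period 2 is considered when insulin treatment is initiated, or alternatively when the patient is discontinued because insulin treatment is not initiated".
- **Period 2 clock.** SAP 2.1.6 ends Period 1 at the confirming failure visit. "The Period 2 start date is defined as the next day".

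The only caveat in the SAP is that the number of patients reaching Period 3 is unknown, so whether the analysis makes sense may need review. That concerns feasibility, not selection.

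**The concern.** A secondary objective in protocol 2.2 is comparative: HbA1c progression in Period 2 under the combination against metformin monotherapy. A slope difference with a p-value will be read as an answer to that objective. But the patients in the model are chosen by what their glucose did after randomisation, and treatment influences both steps of the choice. A small p-value could reflect who was selected rather than how fast the disease progressed. The two data windows add a second problem: two programmers following the same paragraph could analyse different data, and the difference between them is not neutral between the arms.

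**Working it through.** The documents give no slope, SD, sample size or power for this analysis, so there is no stated figure to reproduce. The check is mainly of the text.

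**1. Selection.** Two filters apply after randomisation: HbA1c of at least 7.0% at two consecutive visits (entry to Period 2), then need for intensification under local guidelines. Both are consequences of the path whose slope is estimated.

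A simplified view, ignoring measurement error, shows why the sign of any bias is open. Let c be the level at which insulin is judged necessary (no number is given), E2 the add-on effect in the metformin arm, and T the time left in the study when Period 2 starts. Starting from about 7.0%, a patient reaches c before year 5 only if

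- combination arm: slope ≥ (c − 7.0) / T_C
- metformin arm: slope ≥ (c − 7.0 + E2) / T_M

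The add-on effect raises the bar in the metformin arm. An initial effect of the combination makes a patient with the same underlying path fail later, so T_C tends to be shorter than T_M, which raises the bar in the combination arm. The two forces oppose each other, and c, E2 and the T values are not in the documents.

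**2. The two windows.**

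| Place | Data start |
|---|---|
| Protocol 2.2, 6.4 and 9.5.2.1 | 26 weeks into Period 2 |
| SAP 2.2.3.2 (V3.0 and Addendum 1) | 26 weeks into Period 2 |
| SAP 2.2.3.3, opening sentence of the paragraph | 26 weeks into Period 2 |
| SAP 2.2.3.3, data sentence (also protocol 9.5.2.2) | Start of Period 2 |

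The difference is 26 weeks of data. SAP 2.2.3.1 justifies the Week 26 start of the Period 1 slope by an earlier study in which the largest mean HbA1c reduction came between 24 and 32 weeks. By the same logic, the first 26 weeks of Period 2 are a response phase, and only the metformin arm starts a new drug then.

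**3. Which visit opens the window.** Visits are 13 weeks apart (protocol 3.2). Count days from the failure visit:

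- Period 2 starts on day 1.
- The window opens on day 1 + 26 × 7 = 183.
- The second scheduled visit after failure falls on day 2 × 13 × 7 = 182.

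An on-schedule visit is therefore one day too early. The 28-day windows in SAP 1.3.2 count from treatment start, so they do not settle this.

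**4. Can the effect be sized?** Two illustrative simulations gave both arms the same true slope, with 1000 patients per arm, 13-weekly visits and 4% yearly dropout. They differed in assumed starting HbA1c, slopes, insulin rule and fitting method, none of which the documents fix. With an assumed drug effect of 0.3 HbA1c points, both initially and as add-on, and the 26-week window, the mean slope difference (combination minus metformin) was −0.012 %/year in one and +0.020 %/year in the other. The second also sent about 785 of 1000 metformin patients into Period 2. The plan's own inputs, 10% early failure then 7.1% a year, imply 1 − 0.90 × 0.929^4.75 ≈ 37% before dropout. The disagreement in sign confirms step 1. Neither figure measures the problem.

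**The case against.** The restriction to patients needing intensification is disclosed and follows from how protocol 3.1.3 defines the end of Period 2. The 26-week start appears in every definition, so the data sentence may be loose drafting meant only to limit patients and drop data after insulin. There is one primary endpoint, protocol 9.5.1 names no key secondary, and multiplicity testing has been removed, so all secondary p-values are nominal anyway. The SAP also foresees reviewing whether the analysis is sensible.

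Much of this stands, and it limits the severity. It does not remove the point. SAP 2.1.5 marks its baseline p-values as descriptive, so the authors add that label when they intend it, and they did not add it here. Even as loose drafting, the stated data interval is wrong and needs correcting.

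Three stronger readings are tempting but not supported:

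- **No stop date for patients who leave without insulin.** The opening sentence runs to the end of Period 2, and protocol 3.1.3 defines that end for these patients as their discontinuation.
- **A known false-positive rate or a known favoured arm.** Rates well above 5% can be simulated, but the highest (38–60%) need an add-on effect 2.5 times the initial effect (0.5 against 0.2), which the documents do not support.
- **A fixed share of data lost to the one-day gap.** That assumes every visit falls exactly on day 182. If visits scatter symmetrically around that day, only somewhat more than half fall before day 183.

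**Conclusion.** The point holds on the text. The Period 2 slope difference compares groups formed by events after randomisation, one of which has just started a new drug, and it carries a test and p-value with no descriptive label. One sentence also contradicts the defined data window, and the visit that opens the window is not stated.

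The direction and size of any bias cannot be determined from the documents. A reader might infer that admitting everyone who enters Period 2 would cure the problem. It would not, because entry to Period 2 is itself a post-randomisation outcome. A reader might also infer that the trial's main finding is weakened. It is not: the primary analysis uses the FAS from randomisation and does not touch this model. Severity is minor to should-fix.

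**What to change.** In SAP 2.2.3.3 and protocol 9.5.2.2, for both HbA1c and FPG:

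1. Replace the data interval with the defined one: 26 weeks after Period 2 begins until its end as defined in protocol 3.1.3. State that it opens at the second scheduled visit after the failure visit.
2. Present mean slopes by treatment approach, and their difference, with 95% CIs as descriptive results, and say that the set is defined by events after randomisation. Omit the p-value, or label it nominal and not a randomised comparison. In Addendum 1, also stop calling the reused model that of the primary endpoint.
3. Take any between-arm inference on durability beyond Period 1 from analyses already planned from randomisation. These are time to insulin initiation (protocol Glossary; Addendum 1, 2.2.3.2, with censoring in 2.8) and time to second treatment failure (Addendum 1, 2.2.2.4). The second was added post hoc and should be read as supportive.

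The cost is wording in two documents and the loss or relabelling of these secondary p-values. No new data are needed and the patient set does not change.
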